Official Title: Intense Pulsed Light Study for Dry Eye Disease

NCT03089580

Version Date: July 12th, 2019

A. Study Hypothesis and Objectives

Dry eye disease (DED) is defined as a “multifactorial disease of the tears and ocular surface that results in symptoms of discomfort, visual disturbance, and tear film instability with potential damage to the ocular surface. It is accompanied by increased osmolarity of the tear film and inflammation of the ocular surface[1].” This condition may also compromise surgical outcomes and patient satisfaction following cataract, refractive surgery[2], and corneal transplants[3]. DED can also impact everyday tasks such as reading, using a computer, driving, and watching television which can be up to three times more difficult[4]. Worker productivity is potentially adversely affected by DED and scales with disease severity[5]. In addition, depression is more prevalent in DED patients[6], further evidence of the disease’s debilitating effects. Current treatments options are limited and a recent study found 75% of DED patients report inadequate relief despite treatment. There is a critical barrier to provide efficacious treatment modalities to improve quality of life and to improve ocular surface health affected by DED.

A new treatment called Intense Pulsed Light (IPL) shows promise to reduce signs and symptoms in preliminary studies. IPL is a broad spectrum, non-coherent light treatment applied to the face and lower lids followed immediately by meibomian gland expression. Unfortunately, rigorous peer-reviewed studies on IPL are largely missing. Additional controlled, clinical studies are critical to better understand the potential of IPL to minimize objective measures of DED and improve patient quality of life.

i. Study Aim

The aim of this project is to rigorously evaluate the efficacy of IPL and to determine whether quality of life improvements can result from its implementation. Our hypothesis is that IPL can provide reduction and potential elimination of symptoms for patients with the evaporative form of DED by improving the meibomian gland expression quality and quantity resulting in a more stable, intact tear layer. We believe that the IPL treatment will deliver these results above and beyond meibomian gland expression alone.

ii. Research Goals

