- a.** Substantiate the efficacy of IPL treatment for DED. Our study will collect objective measures of DED disease at baseline and after each of four IPL treatments. Our study design is a prospective, randomized, single masked trial. This evidence will assist practitioners, patients, and third parties to understand the value of this procedure and who will most likely benefit.
- b.** Determine the potential improvement in quality of life measures with IPL. DED has a substantial negative impact on quality of life. We will measure patient symptoms before and after each IPL treatment to assess the change in subjective quality of life measures using two validated questionnaires.
- c.** Demonstrate that IPL treatment improves DED above and beyond meibomian gland expression alone. There is limited evidence to support if the efficacy of IPL treatment is merely from IPL or the meibomian gland expression alone. Our proposed study is intended to clarify whether adding IPL before meibomian gland expression improves the outcomes. To our knowledge, no previous studies have addressed this question.

B. Background Information

Dry eye symptoms are common complaints in an estimated 25% of all eye doctors visits[7]. In the US population over 50 years of age, there are approximately 1.68 million men and 3.23 million women with diagnosed DED[8, 9]. The U.S. healthcare cost attributed to DED is approximately \$3.84 billion[5]. The symptoms of this disease can range from a mild annoyance to extremely debilitating. Common symptoms include burning, stinging, tearing, blurred vision, foreign body sensation, contact lens intolerance, redness, chronic pain, and photophobia. Current treatments include topical tear supplements, environmental modifications to minimize tear evaporation, punctal occlusive treatments, ocular surface barriers, lid treatments, and immunomodulatory agents. Despite these various treatments, inadequate relief is common and there is a critical barrier to provide efficacious treatment modalities to improve quality of life and to improve ocular surface health affected by DED. We propose to test the hypothesis that IPL therapy will provide relief of evaporative DED symptoms by improving meibomian gland expression.

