- a.** Adverse events (AEs) and complications determined by the investigator to be "possibly", "probably" or "definitely" related to the IPL treatment or study procedures will be recorded and reported to the IRB according to their reporting guidelines.
- b.** Any AE that is determined by the investigator to meet the definition of an unanticipated problem involving risks to subjects or others will be reported within 7 days to the IRB if is determined to be a serious problem. If the unanticipated problem is determined to be non-serious, it will be reported to the IRB within 14 days.

ii. Serious Adverse Events

- a.** Any AE which meets the FDA definition of serious and determined by the investigator to be "possibly", "probably" or "definitely" related to the IPL treatment or study procedures will be recorded and reported to the IRB within 7 days.

iii. Other Reportable Occurrences

- a.** All protocol deviations will be reported to the IRB at the continuing renewal.
- b.** Any privacy violation or breach of confidentiality will be reported to the IRB within 7 days and within 24 hours to the UMHS Privacy Office.

iv. Unmasking

- a.** Unmasking of the participant will occur after completion of the ODSDI and NEI-VFQ questionnaires during the 7 month follow up call.
- b.** Unmasking may occur at any time point throughout the trial if it is determined by an investigator to be in the best interest of the participant.

E. Statistical Methods

i. Sample Size and Power

The primary study outcome (pre to post change in TBUT within the treated eye and also the untreated, control eye) dictated the use of a paired statistical approach to sample size estimation. Based on our preliminary data, other published dry eye studies[17], and recent meeting abstract (ASCRS 2014; Gupta PK et al.) the expected, clinically relevant pre to post TBUT increase of 3 seconds with a standard deviation of 4.5 seconds was used. Type I and II error estimates used were standard for a non-pivotal study, 0.05 & 0.20. The estimated the sample size needed detect this difference in TBUT is 27 subjects. We will recruit 30 subjects allowing for an anticipated 10% drop-out rate.

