All three study goals have a paired design wherein the first two goals contrast pre- to post-treatment measures in the treated eye, and the 3rd compares the treated eye to the control eye. The primary analysis for each objective will apply the paired, Student's t-test to contrast the continuous outcome variables for efficacy assessment (TBUT, Shirmer's test, corneal staining) in the treated eye (Goal 1) and the patient's quality of life (Goal 2), and the treated vs. control eye measures (Goal 3) from pre-treatment to post-4th treatment times. If the parametric assumptions of this test are not met, the non-parametric equivalent test, the Wilcoxon signed rank test, will be applied. In all cases, the null hypothesis to be tested is one of no change from pre- to post treatment, with a Type I error probability of 0.05 for the primary outcome assessment. The pattern of change over the 4 treatment visits in these continuous variables will be assessed using mixed, linear regression. SAS version 9.4 statistical software (SAS Institute, Cary, NC) will be used.

F. Summary and Long-Term Plan

Dry eye disease is a prevalent ocular condition with inadequate treatments available for proper relief. IPL has the potential to help those with evaporative dry eye due to meibomian gland dysfunction. This is a new treatment that needs to be studied with more rigor to understand the magnitude of the benefit for the relief of symptoms and reduced clinical signs. This study will provide answers to these questions in a prospective, masked design with the hope of providing an improved quality of life to those with DED.

We plan to use the anticipated results from this pilot study to apply for funding for a larger, prospective study on a specific population at high risk for severe DED, those with graft versus host disease. These patients often have extreme dry eye due to damage to the lacrimal and meibomian glands. Kellogg Eye Center has a large volume of these patients from the University of Michigan Cancer Center. Often the current dry eye treatments are not sufficient to effectively treat their DED. There are currently no studies on the efficacy of IPL on this population. This project would require additional funding through another grant. With addition funding, we also

hope to purchase a meibographer to image the entire meibomian glands in the tarsal plate to detect atrophic glands which are unlikely to respond to treatment.

G. References:

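### The randomised treated-versus-control TBUT contrast is neither the named primary outcome nor the sizing basis and has the wrong null, while Goal 1 allows an uncontrolled before-after efficacy claim

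*Combined protocol and SAP*

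**What the plan says.** - **Primary outcome and sizing (E.i, Sample Size and Power).** The section begins "The primary study outcome (pre to post change in TBUT within the treated eye and also the untreated, control eye" and goes on to sample size: "the expected, clinically relevant pre to post TBUT increase of 3 seconds with a standard deviation of 4.5 seconds was used". It arrives at 27 subjects, with 30 recruited for 10% drop-out. It gives no treated-minus-control difference, no SD for one, and no correlation between the two eyes' changes.
- **Analyses (paragraph following E.i).** The goals are described thus: "the first two goals contrast pre- to post-treatment measures in the treated eye, and the 3rd compares the treated eye to the control eye". Each goal has its own primary analysis, a paired t-test with a Wilcoxon signed rank fallback. For the randomised comparison the text is "the treated vs. control eye measures (Goal 3) from pre-treatment to post-4th treatment times". One null is then set for every goal: "In all cases, the null hypothesis to be tested is one of no change from pre- to post treatment".
- **Goals (A.ii).** Goal a is headed "Substantiate the efficacy of IPL treatment for DED", and its text adds "This evidence will assist practitioners, patients, and third parties to understand the value of this procedure". Goal c asks whether IPL adds to gland expression alone.
- **Treatment of the two eyes (C.iii.c, Post-Treatment).** The lids of both eyes are expressed after the IPL and sham applications. The inclusion criteria also require current dry eye treatments to continue.
- **Questionnaires.** C. Study Design lists the Ocular Surface Disease Index (OSDI) with TBUT as a primary outcome measure. C.ii, Study Procedures, says that the surveys cannot be split by eye.

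**The concern.** Randomisation and the sham protect only the comparison between eyes. That comparison is planned, but three things weaken it.

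1. The named primary outcome and the sample size concern change within an eye.
2. The stated null is wrong for Goal 3. If both eyes improve equally, the hypothesis of no pre-to-post change is false although IPL has added nothing.
3. Goal 1 carries the efficacy label but has no control. A rise in the treated eye could come from IPL, gland expression, continued treatment, regression to the mean or the passage of time.

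If Goal 1 is significant and Goal 3 is not, the plan does not say which result decides whether IPL works. OSDI has a related weakness: it is a primary measure with no concurrent control.

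The Goal 1 text looks to practitioners, patients and third parties as users of the evidence, and section F plans a funding application on the results. The main conclusion could therefore rest on a comparison that ignores the trial's own randomisation.

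**Working it through.** **Inputs from E.i and the analysis paragraph:** pre-to-post rise 3 s, SD 4.5 s, alpha 0.05, power 80%, 27 evaluable, 30 recruited. Sidedness is not stated; two-sided is used here.

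**Assumptions (not in the documents):** a common improvement *c* of 1, 2 or 3 s in both eyes with no IPL effect, and a between-eye correlation of changes *r* from 0 to 0.8.

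**1. The plan's own figure.** Normal approximation for a paired test: n = ((1.96 + 0.84) × 4.5 / 3)² ≈ 17.7, so 18. The exact paired t-test (noncentral t) needs 20 (power 80.7%; 19 gives 78.5%). The stated 27 does not reproduce at 80% power if 4.5 s is the SD of change, which E.i does not say. With 27 the power would be 91.5%. The SD of change that makes 27 give exactly 80% for 3 s is 5.36 s, so both SDs are carried below. The drop-out step does reproduce: 27 / 0.9 = 30.

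**2. Goal 1 when IPL adds nothing.** Paired t-test on the treated eye, n = 27, noncentrality = (c / SD) × √27. The joint outcome comes from simulation (200,000 trials per case, r = 0 and 0.5).

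| Common change in both eyes | Goal 1 significant, SD 4.5 | Goal 1 significant, SD 5.36 | Goal 1 significant and Goal 3 not, SD 4.5 | Same, SD 5.36 |
|---|---|---|---|---|
| 1 s | 20% | 15% | about 18% | about 14% |
| 2 s | 60% | 46% | about 58% | about 44% |
| 3 s | 92% | 80% | about 87% | about 77% |

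The between-eye test rejects in 4.9% to 5.1% of simulated trials, its nominal rate.

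**3. What 27 patients deliver for the between-eye contrast.** If both eyes' changes have the same SD, the SD of their difference is SD × √(2(1 − r)). For SD 4.5 and r = 0 this is 4.5 × √2 = 6.36 s.

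| r | Detectable at 80% power, SD 4.5 | Detectable, SD 5.36 | Power for 3 s, SD 4.5 | Power for 3 s, SD 5.36 |
|---|---|---|---|---|
| 0 | 3.6 s | 4.2 s | 66% | 51% |
| 0.3 | 3.0 s | 3.5 s | 81% | 66% |
| 0.5 | 2.5 s | 3.0 s | 92% | 80% |
| 0.8 | 1.6 s | 1.9 s | over 99% | 99% |

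The 3 s in the plan is a pre-to-post rise. The between-eye difference would be smaller if the control eye also improves. For an assumed 1.5 s difference, power runs from 22% (r = 0) to 75% (r = 0.8) with SD 4.5 s, and from 17% to 60% with SD 5.36 s.

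**The case against.** The strongest reply is that the randomised contrast is already prespecified. Goal 3 has its own primary analysis, section A states the hypothesis as benefit beyond expression alone, and goal c takes up the attribution question. Section A also describes IPL as light "followed immediately by meibomian gland expression". On that reading Goal 1 asks whether the package improves the eye and Goal 3 isolates the light, so a positive Goal 1 with a null Goal 3 is interpretable. The null may be loose drafting, since a paired test of treated against control change in practice tests a zero difference. The study calls itself non-pivotal and a pilot, and both eyes' TBUT is recorded at every clinic visit, so nothing is lost.

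Much of this stands. The contrast is not missing, and underpowering is not shown: with SD 4.5 s, 27 patients give about 80% power for a 3 s between-eye difference at r = 0.3. The 20%, 60% and 92% are not type I errors of Goal 1's own null, because in those scenarios the eye really changed. The error lies in crediting the change to IPL. The 3 s case is also the extreme one, with the control eye improving by the whole expected rise. The sentence about practitioners and third parties may refer to the trial as a whole.

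The package reading does not rescue Goal 1, because an uncontrolled before-after change cannot establish efficacy of a package either. The goals remain unranked, and the written null still contradicts the Goal 3 description in the same paragraph.

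**Conclusion.** The concern holds, and the text must be corrected. The plan includes the right comparison but attaches its primary outcome and sample size to a different one, states a null that does not fit it, and lets an efficacy claim rest on a before-after test. With no IPL effect and an equal 1 to 3 s improvement in both eyes, Goal 1 would be significant while Goal 3 is not in about 18% to 87% of trials (SD 4.5 s) or 14% to 77% (SD 5.36 s). These rates rest on assumed control-eye changes, 27 evaluable patients and two-sided testing at 0.05; 5.36 s is back-calculated from the stated sample size. The conflict in the text does not depend on any of these assumptions.

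**What to change.** 1. In E.i and the analysis paragraph, define the primary TBUT analysis as the within-patient difference, treated minus control eye, in change from baseline to visit 5, two-sided at 0.05, with a null of no difference between eyes in change. Confine the no-change null to the within-eye and questionnaire analyses.
2. Report within-eye TBUT changes with 95% confidence intervals as descriptive. Base any statement that IPL is effective, under Goal 1 or Goal 3, on the between-eye contrast.
3. Keep N at 30. Say whether 4.5 s is the SD of change, and restate what 27 evaluable patients deliver for the between-eye contrast under a stated correlation. Do not carry the 3 s over as the between-eye effect without justification.
4. State that OSDI and the NEI-VFQ are uncontrolled pre-to-post measures whose change cannot be attributed to IPL.

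**Cost.** No new patients, visits or data; only the primary outcome, null and power text change. The within-eye p-value can no longer be the headline, OSDI change cannot support an IPL claim, and the stated power may look worse: for a 3 s between-eye difference at r = 0 it is 66% or 51%, depending on the SD.

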Appendix A: Schedule of Events

Procedure	Baseline (Visit 1)	1 week phone call (+/- 2 days)	Visit 2, 4.5 weeks (+/- 10 days)	Visit 3, 8.5 weeks (+/- 10 days)	Visit 4, 12.5 weeks (+/- 10 days)	Visit 5, 16.5 weeks (+/- 10 days)	7 month phone call (+/- 5 days)	Optional Visit (e)
Informed Consent (a)	X							
Pregnancy Test (a)	X							
Review of Systems (a)	X		X	X	X	X		
Ocular and Systemic Medications (a)	X		X	X	X	X		
Adverse Event Assessment (a)		X	X	X	X	X		
Pinholed ETDRS Visual Acuity (a)	X		X	X	X	X		X(f)
OSDI Questionnaire (a)	X		X	X	X	X	X	
NEI-VFQ Questionnaire (a)	X		X	X	X	X	X	
Tear Osmolarity (a)	X						X	
Eyelid Photography at Slit Lamp (a)	X						X	
Facial Photography (a)	X						X	
Meibography (a,c)	X						X	
TBUT (b)	X		X	X	X	X		X
Fluorescein Staining (b)	X		X	X	X	X		X
Lissamine Green Staining (b)	X		X	X	X	X		
Meibomian Gland Evaluation (b)	X		X	X	X	X		

Schirmers Test (c)	X		X	X	X	X		
Intraocular Pressure Measurement (c)	X		X	X	X	X		
Randomization (c)	X							
Unmasking (d)							X	
IPL and Sham Treatment (c)	X		X	X	X			X (IPL to both eyes)
Expression of Upper and Lower Lids (c)	X		X	X	X			X
Begin ketorolac Instillation (twice a day for three days) (c)	X		X	X	X			X

** All tests are completed on both eyes except that IPL treatment is performed on one eye and the sham treatment is performed on the other.

** Fluorescein staining, lissamine green staining and Meibomian gland evaluation are to be completed right eye and then left eye.

- a- Indicates that it is to be completed by study coordinator/technician (excludes the optional visit).
- b- Indicates that it is to be completed by a masked corneal specialist (excludes the optional visit).
- c- Indicates that it is to be completed by the unmasked PI.
- d- Unmasking of the participant will occur after completion of the ODSDI and NEI-VFQ questionnaires.
Unmasking may occur at any time point throughout the trial if it is determined by an investigator to be in the best interest of the participant.
- e- Can be completed entirely by Unmasked PI
- f- ETDRS visual acuity testing may be substituted for standard Snellen visual acuity at optional visit

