There are two classifications of DED: aqueous deficient and evaporative[1]. There is some overlap, but the vast majority of dry eye is evaporative. Meibomian gland dysfunction (MGD) is the most common cause of evaporative dry eye. Intense Pulsed Light (DermaMed Solutions, Lenni, PA; Lumenis Ltd., Yokneam, Israel) will be applied to the lower eyelids and face with the intent to improve MGD. We will test our hypothesis and complete our goals by conducting an intervention to one eye and the fellow eye will serve as a control to compare the effects of IPL in patients who have evaporative DED due to MGD.

The study is a prospective, randomized, controlled, single masked trial. The randomization is based on IPL treatment to one eye and sham treatment to the fellow eye. The randomization will occur via a random number generator. The masking is based upon the cornea specialist's examination. The primary outcome measures include tear break up time (TBUT) and the Ocular Surface Disease Index (OSDI) symptom survey. Exploratory outcome measures will include the National Eye Institute Visual Function Questionnaire (NEI-VFQ), changes in MGD quantitated by lid margin photography and meibography before and after IPL, and other standard dry eye clinical evaluation tools.

All enrolled participants will be assigned a number, and the link between the number and participant will be secured. All data collection will comply with HIPPA guidelines. Data collection will include: clinical exam data, eyelid and facial photography, and meibography which will be de-identified.

i. Participant Eligibility Criteria

a. Inclusion Criteria

1. Willing and able to provide informed consent;
2. 18 years of age or older;
3. Diagnosed with evaporative dry eye disease with symptoms for 6 months or more;
4. Able and willing to comply with follow-up visits, phone calls and IPL treatments;
5. Agree to using an effective method of birth control during the course of the study;
6. Agree to continue current dry eye treatments during the course of the study;
7. Fitzpatrick skin scale[14] of 1 (very fair) to 4 (olive) as determined by an investigator.

b. Exclusion Criteria

1. Darker skinned individuals defined by the Fitzpatrick scale 5 and 6 as determined by an investigator;
2. Neurotrophic keratitis;
3. Ectropion, trauma, or any other lid abnormalities;
4. Previous diagnosis of Stevens Johnson syndrome or graft versus host disease;

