The patients will be evaluated at baseline (visit 1) and return once a month for a total of 5 months (visits 2, 3, 4 and 5). They will be asked to complete study testing and will be evaluated by a masked corneal specialist at each visit. The phenotypic characterization for dry eye will include the following tests for both eyes: tear break-up time (TBUT) in triplicate using a timer, lissamine green staining of conjunctiva (grading 1-4, noted temporally and nasally), corneal staining with fluorescein (grading 1-4, breaking the cornea into 4 sections), meibomian gland health with the Meibomian Gland Evaluator (TearScience, Morrisville, NC), tear osmolarity, and 5-minute Shirmers under anesthetic using a timer. All patients will also undergo standardized slit lamp eyelid margin photography that includes upper and lower lids, have facial photography and meibography of the lids. Other testing that will be completed at certain time points include pinholed ETDRS visual acuity testing and the measurement of intraocular pressure. We will also obtain information about the participant's medical history (review of systems), and current ocular and systemic medications.

All participants will take the Ocular Surface Disease Index (OSDI)[15] and 25-item National Eye Institute Visual Functioning Questionnaire (NEI-VFQ)[16]. Both questionnaires will be administered at each visit. These surveys do not allow for separating the response between each eye.

The participants will also be contacted over the phone by a member of the study team approximately 1 week and 7 months after their baseline visit.

iii. Study Design

Once the patient has signed informed consent, completed the baseline testing, and is determined to be eligible by an investigator, they will have one eye randomized to receive the IPL treatment and the fellow eye will receive a sham treatment.

a. Intervention with IPL

IPulse Quadra Q4 and Lumenis M22 devices will be provided by the cornea clinic at Kellogg Eye Center.

Prior to treatment, eye shields will be placed over both eyes of the participant. On the side that was randomly selected to receive the IPL treatment, ultrasound gel will be applied around the eye, lower eyelid, cheek, side of nose and temple. The PI will then administer approximately 15 light spots in areas where the ultrasound gel was applied.

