All IPL treatments will be performed by the same investigator, the PI, who will not be masked. Each subject's eyes will be randomized with one eye/side of the face receiving IPL treatment (Figure 3), and the fellow eye serving as a control. At the first IPL treatment, the energy level (range of 8-18 joules) will be individually determined based the patient's skin Fitzpatrick scale phototype. The IPL instrument, Quadra Q4®, includes four pulse levels (1-4) each with six sublevels (A-F). The pulse intensity is inversely related to the skin phototype scale, and as noted in subject inclusion and exclusion criteria above, we will only treat patients who are phototype 1 through 4. The sublevel D is used for the initial treatment unless the patient cannot tolerate it and then a lower sublevel will be used. Future treatments sublevels will be increased gradually unless the examiner determines this is unsafe for the patient.

The Lumenis M22 IPL device requires the user to input fluence (joules/cm²) level prior to treatment. The below graph shows the fluence levels of the Dermamed Quadra Q4® that correlate to the fluence levels of the Lumenis M22.

		Fitzpatrick Skin type		
	1	2	3	4
A	10J/cm ²	9J/cm ²	8J/cm ²	8J/cm ²
B	11J/cm ²	10J/cm ²	9J/cm ²	8.5J/cm ²
C	12J/cm ²	11J/cm ²	9.5J/cm ²	9J/cm ²
D	13J/cm ²	12J/cm ²	10J/cm ²	9.5J/cm ²
E	14J/cm ²	13J/cm ²	10.5J/cm ²	10J/cm ²
F	15J/cm ²	14J/cm ²	11J/cm ²	10.5J/cm ²

Figure 3. IPL treatment. After placing eye shields, an ultrasound gel is applied. Treatment spots are done around the eye, lower eyelid, cheek, side of nose and temple.

b. Sham Treatment

With the eye shields still in place, the fellow eye will be treated with approximately 15 spots of pressure around the eye, lower eyelid, cheek, side of nose and temple with the IPL device. No light energy will be applied. The PI will only place the device on the participant and press to mimic actual IPL treatment. Ultrasound gel will be applied to these areas prior to the sham treatment to prevent unmasking of the participant.

c. Post-Treatment

After the IPL and sham treatments have been completed, the eye shields will be removed, and the face cleaned. The upper and lower lids of both eyes will be expressed with a meibomian gland expressor while being positioned at the slit lamp.

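### Schirmer's test, one of three named efficacy variables, is measured only by the unmasked PI who randomises and treats the eyes

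*Combined protocol and SAP*

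**What the plan says.** - **Role in the analysis.** The analysis paragraph under E. Statistical Methods applies the paired t-test to "the continuous outcome variables for efficacy assessment (TBUT, Shirmer's test, corneal staining) in the treated eye (Goal 1"), and to the same kind of measures in treated versus control eyes for Goal 3. The change runs from before treatment to after the fourth treatment.
- **Outcome tier.** Section C. Study Design states: "The primary outcome measures include tear break up time (TBUT) and the Ocular Surface Disease Index (OSDI) symptom survey". Schirmer's is not among them. The next sentence of that section puts other standard dry eye tests in the exploratory group.
- **Who measures it.** In Appendix A the row reads "Schirmers Test (c"), marked at baseline and visits 2 to 5. Footnote c: "Indicates that it is to be completed by the unmasked PI". The rows for TBUT, fluorescein staining and lissamine green staining carry (b), the masked corneal specialist.
- **What else that person does.** Randomisation and the IPL and sham treatments are also coded (c). Section C.iii.a adds: "All IPL treatments will be performed by the same investigator, the PI, who will not be masked".
- **Scope of masking.** Section C: "The masking is based upon the cornea specialist's examination".
- **The test itself.** Section C.ii lists a "5-minute Shirmers under anesthetic using a timer" among the dry eye tests. It says a masked specialist evaluates patients at each visit, but does not say who performs each test.
- **Timing of randomisation.** Section C.iii: once a patient has "completed the baseline testing, and is determined to be eligible by an investigator, they will have one eye randomized to receive the IPL treatment".

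**The concern.** The design compares two eyes of the same person, one given IPL and one given sham. That contrast is credible only if both eyes are measured in the same way. For Schirmer's, the person measuring knows which side received IPL and has treated it personally. By the assessment after the fourth treatment, that person has treated it four times.

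Baseline testing comes before randomisation, so knowledge of the side cannot affect the baseline reading. It can affect only the follow-up readings. Any resulting error would therefore not cancel between baseline and follow-up. It would pass straight into the change score for the treated eye (Goal 1) and into the difference in change between eyes (Goal 3).

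Goal 3 asks whether IPL adds anything to meibomian gland expression alone, which the protocol presents as its new question. A Schirmer's difference in favour of IPL could not be cleanly separated from assessor expectation, while a difference in TBUT or staining would not have this weakness.

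**Working it through.** **Step 1. Set the efficacy variables beside the assessor codes.**

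| Variable named in section E | Code in Appendix A | Assessor, visits 1 to 5 |
|---|---|---|
| TBUT | (b) | masked corneal specialist |
| Corneal (fluorescein) staining | (b) | masked corneal specialist |
| Schirmer's test | (c) | unmasked PI |

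Two of the three are masked and one is not. The schedule uses a joint code where two people share a task (meibography is coded a,c), so a lone (c) means the PI alone. No section provides a masked second reader for Schirmer's.

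**Step 2. Where bias can enter.** Let *b* be a systematic error in the follow-up readings that favours the treated eye, with no such error at baseline. If IPL has no effect, the expected between-eye difference in change is *b*, not 0.

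**Step 3. What a given *b* would do to the Goal 3 test (illustration).** The plan gives no figure of its own to reproduce.

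- Number of subjects: n = 27 (computed sample size) or 30 (planned recruitment), both from section E.i.
- Test: paired t, two-sided 0.05. The plan sets 0.05 for the primary outcome; using it for Schirmer's, and taking it as two-sided, are assumptions.
- Bias: d = *b* divided by the SD of the between-eye difference in change. All values of d are assumed.

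The rejection probability with no true effect is P(|T| > t₀.₉₇₅,ₙ₋₁), where T is noncentral t with n − 1 degrees of freedom and noncentrality d√n. The critical value is 2.056 for n = 27 and 2.045 for n = 30. For example, d = 0.2 and n = 27 give a noncentrality of 0.2 × √27 = 1.039 and a rejection probability of 0.170.

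| Assumed d | n = 27 | n = 30 |
|---|---|---|
| 0 | 5.0% | 5.0% |
| 0.05 | 5.7% | 5.8% |
| 0.1 | 7.9% | 8.3% |
| 0.2 | 17.0% | 18.5% |
| 0.3 | 32.4% | 35.6% |

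The rate reaches 10%, twice nominal, at d = 0.130 (n = 27) or d = 0.123 (n = 30). These figures apply to the between-eye comparison only.

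**Step 4. Time needed to move the test to the masked specialist.** 5 minutes × 5 visits × 30 subjects = 750 minutes = 12.5 hours if both eyes are tested together. If they are tested one after the other, the total is 2 × 12.5 = 25 hours.

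**The case against.** The strongest reply has four parts.

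1. *Schirmer's ranks low.* It is not primary, section C's wording most naturally makes it exploratory, and the protocol calls itself a pilot. This stands, and it limits the importance of the point. But section E lists Schirmer's beside TBUT and staining in the primary analysis for each objective, so a reader would give the three equal standing.
2. *The test leaves little room for influence.* It has a fixed duration and uses a timer. This reduces the risk. It does not remove it, because a timer fixes duration and not how the strip is placed or read. TBUT is also timed, yet it was given a masked assessor.
3. *The limit is disclosed.* The trial is described as single masked, masking is tied to the specialist's examination, Appendix A calls the PI unmasked, and section C.iii.e refers to Appendix A for the testing at follow-up visits. So this is a design choice and not a contradiction. Disclosure does not protect the measurement.
4. *The illustration is generic.* Nothing in it is specific to Schirmer's, and very small biases do little harm: 5.7% to 5.8% at 0.05 SD. This is correct. The table shows how sensitive the test is to bias; it does not show that bias exists.

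Two practical objections also stand. The hours in Step 4 leave out anaesthetic, set-up and recording. And if any participant already has a baseline measured by the PI, recoding would change the assessor between baseline and follow-up.

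**Conclusion.** The concern holds. One of the three efficacy variables named for the paired analyses is assessed only by the person who randomises and treats the eyes, with no masked reader. The other two are assessed under masking.

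This rests on the assignments in Appendix A and the list in section E, and needs no numerical assumption. How much bias would result cannot be estimated from the documents. If it were 0.1 to 0.3 SD of the between-eye difference, the Goal 3 false-positive rate for Schirmer's would be about 8% to 36% across n = 27 and n = 30; nearer zero it would stay close to 5%.

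The effect is confined to Schirmer's. TBUT, staining and the sample size are untouched. It is a worthwhile and inexpensive improvement, not a flaw in the primary comparison.

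**What to change.** In Appendix A, change the code for Schirmer's from (c) to (b). The masked corneal specialist already examines at visits 1 to 5, so no staff are added. Code (a) would serve only if footnote a were amended to say that the coordinator or technician is masked to the treated side, which it does not say now. As an editorial matter, section C.ii could also state who performs each test.

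If recoding is not practical, say in section E that Schirmer's is an unmasked, supportive outcome, and report it apart from TBUT and staining. The same labelling suits any participant whose baseline was already measured by the PI, because a change of assessor would otherwise be mixed into the Goal 1 change. The documents do not give enrolment status.

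The cost is an edit to the appendix and text, plus 12.5 to 25 hours of specialist test time over the trial and some set-up time. The PI's time falls by a similar amount. Treatment, outcomes and sample size do not change.
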